# **Application of Carbon Dioxide for Identifying the Intersegmental Plane in Thoracoscopic Segmentectomy: A Randomized Controlled Study**

**Registration number: NCT05350137**

**Date: June 15, 2023**

## **Study Protocol**

This study was a prospective, single-center, open-label, randomized controlled trial.

This study was registered at ClinicalTrials.gov (NCT05350137), and has received the stamp of approval from the ethics committee of Tongji Hospital, Tongji Medical College, Huazhong University of Science and Technology (NO: TJ-IRB20220140). All enrolled patients signed the informed consent form.

### **Inclusion Criteria:**

1. 18-80 years of age.
2. Segmentectomy is feasible according to the reconstructed 3-dimensional (3D) images.
3. Pulmonary nodule 2 cm or smaller in diameter with 50% or more ground-glass opacity (GGO) on thin-slice computed tomography, indicating an underlying malignancy.
4. Ability to provide written informed consent.
5. Unable to tolerate lobectomy as indicated by standard clinical pre-op evaluation, including pulmonary function tests and cardiac evaluation.
6. Diagnosis confirmed or suspected of lung metastatic cancer.

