### **Exclusion Criteria:**

1. Patients who are at risk for general anesthesia.
2. Patients with serious mental illness.
3. Pregnancy or lactating women.
4. Active bacterial or fungal infections.
5. Patients with Interstitial pneumonia, pulmonary fibrosis or severe emphysema.
6. Conversion to thoracotomy in surgery.
7. Preoperative assessment of patients undergoing lobectomy.

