## **Randomization**

The patients were randomly assigned to the CO2 group and O2 group at a 1:1 ratio. 52 opaque envelopes were made according to a random table generated by the PLAN process of SAS (SAS9.4, SAS Institute Inc). Each patient would receive an envelope which was opened by operators in surgery, when the structures of targeted segment were successfully dissected and anesthesiologist was about to re-expand the collapsed lung.

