## Outcome Measures

**Primary outcome:** The intersegmental border appearance time during the surgery.

**Secondary outcome:** Including BIS, arterial blood gases, arterial pressure and heart rate obtained when the patient was breathing room air (RA), the non-dependent lung was ready to be re-expanded when the bronchi and vessels of targeted segment had been dissected (0min), 3, 5, and 15 min after the non-dependent lung was fully inflated. Besides that, end-tidal carbon dioxide partial pressure (PetCO2) at 0, 3, 5, 15 min, duration of surgery, duration of drainage, total drainage, postoperative hospital stay, global Quality of Recovery 40 questionnaire (QoR-40) at 48 hours and 1 week after operation, postoperative complications (such as air leakage, pneumonia, atrial fibrillation, and all the postoperative complications were classified by the Clavien-Dindo classification of adverse events) were also included as secondary outcomes.

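### Do the inclusion criteria need an explicit and/or rule for items 3, 5 and 6?

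*Combined protocol and SAP*

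**What the plan says.** The Inclusion Criteria section has six numbered items. Items 1 and 4 (age and consent) plainly apply to everyone, and so does item 2, "Segmentectomy is feasible according to the reconstructed 3-dimensional (3D) images". The other three are:

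- item 3: "Pulmonary nodule 2 cm or smaller in diameter with 50% or more ground-glass opacity (GGO) on thin-slice computed tomography", taken as a sign of malignancy;
- item 5: "Unable to tolerate lobectomy as indicated by standard clinical pre-op evaluation, including pulmonary function tests and cardiac evaluation";
- item 6: "Diagnosis confirmed or suspected of lung metastatic cancer".

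No connecting word stands between the items, and no other section says how they combine.

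Item 7 of the Exclusion Criteria reads "Preoperative assessment of patients undergoing lobectomy". The phrase is awkward. Its most natural sense is that patients judged before surgery to be going for lobectomy are not eligible.

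The Randomization section says that "52 opaque envelopes were made according to a random table", with 1:1 allocation, and that each envelope was "opened by operators in surgery, when the structures of targeted segment were successfully dissected".

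**The concern.** A numbered inclusion list is by convention cumulative. Taken that way, each participant must have a small, predominantly ground-glass nodule, be unfit for lobectomy, and have known or suspected metastatic disease. These read more like three separate reasons for a segmentectomy than one patient profile. Exclusion 7 adds to the doubt: if everyone enrolled is already unable to tolerate lobectomy, there is nobody left for it to exclude. It is tempting to conclude that the three items must be alternatives and that the plan should say so.

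The stake would be the population to which the secondary results apply. Item 5 is defined by lung function and cardiac evaluation. The Outcome Measures section collects "BIS, arterial blood gases, arterial pressure and heart rate obtained when the patient was breathing room air" and repeats these measurements at set times around re-expansion of the lung. A reader of blood gas and haemodynamic results after CO2 or O2 inflation would want to know whether they come from patients with limited cardiorespiratory reserve.

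**Working it through.** The plan states no figure on this point, so there is none to reproduce. The check is of the eligibility logic.

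**Step 1: what exclusion 7 can tell us.** Each of items 3, 5 and 6 is met or not met, which gives 2 × 2 × 2 = 8 patient profiles. Assume that a patient who meets item 5 is never assessed for lobectomy. Exclusion 7 can then act only on an admitted profile in which item 5 is not met. Nine ways of combining the items give:

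| Rule | Profiles admitted (of 8) | Admitted with item 5 not met |
|---|---|---|
| 3 and 5 and 6 | 1 | 0 |
| (3 or 6) and 5 | 3 | 0 |
| 3 and (5 or 6) | 3 | 1 |
| (3 or 5) and 6 | 3 | 1 |
| (3 and 6) or 5 | 5 | 1 |
| (3 and 5) or 6 | 5 | 2 |
| 3 or (5 and 6) | 5 | 2 |
| 3 or 6, item 5 ignored | 6 | 3 |
| 3 or 5 or 6 | 7 | 3 |

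Exclusion 7 is idle under the two rules that require item 5 of everyone and can act under the other seven. It is therefore some evidence that item 5 was not universal. It does not separate the remaining seven rules, and it says nothing about how items 3 and 6 relate.

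**Step 2: whether an idle exclusion is an inconsistency.** It is not. Exclusion lists often restate the scope of a trial. This trial is titled as a study of segmentectomy, so a patient scheduled for lobectomy is arguably outside it under every rule in the table. Exclusion 7 can be redundant without conflicting with any inclusion item.

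**Step 3: whether the rule can disturb the comparison.** Age, imaging, consent, fitness for lobectomy and known or suspected diagnosis are all facts available before the operation. The envelope is opened during surgery, after dissection. The Randomization section does not say when eligibility was checked, but the content of the items makes a preoperative check the reasonable inference. The rule, whichever it was, then acts before the arm is known and equally on both arms.

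**Step 4: the size of what is unknown.** If all 52 envelopes are used, 52 of 52 patients meet item 5 when it is required, and anywhere from 0 to 52 when it is not. An exact 1:1 split gives 52 / 2 = 26 per arm. For a difference in means between arms within item-5 patients, with n per arm, the 95% half-width in SD units is t(0.975, 2n − 2) × √(2/n):

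- n = 26: 2.0086 × 0.2774 = 0.56
- n = 13: 2.0639 × 0.3922 = 0.81
- n = 5: 2.3060 × 0.6325 = 1.46

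The values 13 and 5 only mark points in the possible range. These half-widths describe the precision of an item-5 subgroup contrast, and the Statistical analysis section plans no such contrast. They do not measure any error in the planned analyses.

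**The case for a change.** The best case for a change is that it would cost little and that the text really is open. One sentence would settle the rule, and one baseline row would show how many patients met item 5. If enrolment is complete, the extra work is classifying at most 52 charts. Two other exclusions also sit uneasily with a rule that makes everyone unfit for lobectomy: exclusion 1 (anesthetic risk) and exclusion 5 (severe emphysema, interstitial pneumonia, fibrosis). A reader of the secondary results has a fair interest in knowing how much cardiorespiratory impairment was present.

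Part of this stands. The missing connector is a genuine omission, and a count by indication would be informative if the trial report gave it. It does not amount to a reason to alter the plan. Exclusions 1 and 5 do not contradict item 5, since tolerance of lobectomy and anesthetic risk are different judgements. They also cut the other way, because they limit severe impairment under any reading. The Statistical analysis section already provides for describing baseline characteristics, although it does not list the variables. Finally, the documents do not establish which combination was meant. To write in at least one of 3, 5 or 6 would choose an indication for segmentectomy on the investigators' behalf. The document describes randomization and consent in the past tense, so a rule inserted now could also misstate the one actually applied.

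**Conclusion.** No change to the plan is called for. The list leaves out its and/or rule, and exclusion 7 on its natural reading is redundant if item 5 is universal. This is missing detail of a kind that investigators selecting patients for segmentectomy can be expected to fill sensibly. The claim that the items must be alternatives is not proved: seven of the nine rules examined leave exclusion 7 with work to do, and a redundant exclusion would be harmless in any case.

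Nothing in the randomized comparison, the number of envelopes, the primary outcome or its analysis depends on the answer. The only effect is on how the enrolled population is described, chiefly the item-5 count (52, or somewhere from 0 to 52).

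This rests on four assumptions: exclusion 7 is read as removing patients assessed for lobectomy; a patient unfit for lobectomy is not so assessed; eligibility on these items was settled before the envelope was opened; and all 52 envelopes were used. The third carries the most weight and is inferred from the nature of the items, since the text does not state it.

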## **Statistical analysis**

The demographic and baseline characteristics of the patients, vital signs, TISP, arterial blood gas indexes, and the perioperative outcomes could be divided into two types: categorical variables and continuous variables. The categorical variables were expressed by frequencies and proportions, and were analyzed by chi-square test or continuity correction chi-square test. The continuous variables were expressed by mean  $\pm$  SD, and were analyzed by t test or Fisher's exact test. All statistical analyses were 2 sided, and  $p < 0.05$  was considered statistically significant. Statistical analyses were performed by SPSS (IBM SPSS 28.0, SPSS Inc).

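### The primary comparison of border appearance time is a valid but unadjusted t test; one preoperative lung-function covariate could sharpen it at almost no cost, if lung function predicts that time

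*Combined protocol and SAP*

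**What the plan says.** The Inclusion Criteria are six numbered items with no connecting word to show which must hold together. Item 3 concerns a small nodule: "Pulmonary nodule 2 cm or smaller in diameter with 50% or more ground-glass opacity (GGO) on thin-slice computed tomography". Item 5 covers patients "Unable to tolerate lobectomy as indicated by standard clinical pre-op evaluation, including pulmonary function tests and cardiac evaluation". Item 6 reads "Diagnosis confirmed or suspected of lung metastatic cancer". Items 3 and 6 put no limit on lung function. Item 5 of the Exclusion Criteria narrows the range by removing "Patients with Interstitial pneumonia, pulmonary fibrosis or severe emphysema"; less severe emphysema is not mentioned there.

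On allocation, the Randomization section says "The patients were randomly assigned to the CO2 group and O2 group at a 1:1 ratio" and "52 opaque envelopes were made according to a random table generated by the PLAN process of SAS". It names no stratification factor.

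The primary outcome is "The intersegmental border appearance time during the surgery". The Statistical analysis section lists this time (as TISP) among the variables and assigns continuous variables a t test or Fisher's exact test. For a continuous time, the t test is the workable reading. No covariate or regression model is named for any outcome. Pulmonary function tests appear only inside inclusion item 5.

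**The concern.** The outcome is a time observed after the lung on the operated side is re-expanded with one of two gases. It is plausible, though not stated in the documents, that the condition of the airways and lung tissue affects how quickly the border shows. If so, two things follow.

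First, variation between patients that a preoperative measurement could explain stays in the error term of the primary test. Precision matters here because 52 is given without an effect, SD or power to justify it.

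Second, with about 26 patients per arm, one arm may by chance receive more patients with reduced lung function. The unadjusted difference then carries part of that imbalance, and the plan has no analysis that removes it.

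**Working it through.** **Inputs from the documents.** 52 envelopes, 1:1 allocation, two-sided 0.05. I take 26 per arm.

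**Inputs assumed, because the documents give none.** R², the share of within-arm variance of border time explained by one lung-function covariate: 0 to 0.3. Number of patients with impaired lungs: 10 to 21 of 52 (19% to 40%).

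**The plan's own figure.** 52 cannot be reproduced, since no effect, SD or power is stated. Solving backwards, with 26 per arm the t test has 80% power for a difference of (1.96 + 0.84) × √(2/26) = 0.78 SD, or 0.79 SD by the noncentral t.

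**1. Precision.** Adjusting for one covariate multiplies the standard error by √[(1 − R²) × (1 + 1/48)]. The second factor is the cost of estimating the covariate's slope. Residual degrees of freedom fall from 50 to 49.

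| Assumed R² | Standard error ratio | Power when the t test has 80% |
|---|---|---|
| 0 | 1.01 | 79% |
| 0.1 | 0.96 | 83% |
| 0.2 | 0.90 | 87% |
| 0.3 | 0.85 | 91% |

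Break-even is where (1 − R²) × 49/48 = 1, so R² = 1/49, about 2% (a correlation of about 0.14).

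**2. Chance imbalance, impaired or not.** If K of 52 patients are impaired and the arms are 26/26, the number k in one arm is hypergeometric, and the arms differ by |2k − K|/26. A gap of 15 points needs a difference of at least 4 patients (4/26 = 15.4%), and 20 points needs at least 6 (6/26 = 23.1%). The difference has the same parity as K, so odd K needs 5 and 7.

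| K impaired | P(gap ≥ 15 points) | P(gap ≥ 20 points) |
|---|---|---|
| 10 | 29% | 8% |
| 11 | 17% | 4% |
| 16 | 37% | 13% |
| 20 | 39% | 15% |
| 21 | 26% | 9% |

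Over every K from 10 to 21 the ranges are 17% to 39% and 4% to 15%. The smallest values occur at K = 11 and the largest at K = 20.

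**3. What an imbalance does to one result.** For a continuous lung-function measure, the standardized difference between arms has standard error √(2/26) = 0.28 SD, so a gap above 0.5 SD has probability 7%. A 0.5 SD gap moves the unadjusted contrast by 0.5 × correlation. That is 0.15 outcome SD at a correlation of 0.3 and 0.25 at 0.5, or 0.15/0.277 = 0.54 and 0.25/0.277 = 0.90 of the contrast's standard error.

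**The case against.** The strongest reply is that nothing in the plan is invalid. Randomization makes the unadjusted t test unbiased, its type I error holds, and its standard error already allows for chance imbalance. An unstratified, unadjusted comparison is an acceptable choice in a 52-patient single-center trial. All of this stands, and it limits the point to efficiency and to the interpretation of a single result.

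A reader might go further and infer that the comparison is in fact noisier than it needs to be. The documents do not support that. They give no correlation between lung function and border time, and exclusion item 5 states no reason, so it does not show that the sponsor links lung structure to this outcome. At R² below about 2% there is no gain.

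The mix of normal and impaired lungs is also an inference. It depends on reading items 3, 5 and 6 as alternatives, which is the practical reading but is not stated, and exclusion item 5 narrows it.

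A reader might also conclude that allocation should have been stratified by item 5. That would not balance lung function, because item 5 also admits patients on cardiac grounds. The past tense of the Randomization section suggests, too, that the envelopes already exist.

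Finally, the plan names no particular lung-function measure and does not confirm that one was recorded for every patient. A whole-lung measure may also say little about the border of a single segment. These are real limits on the gain, and the fix has to be conditional on the data being there. They do not remove the case for adjustment, since the loss if the covariate is useless is about 1% in standard error.

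**Conclusion.** The point holds as a conditional efficiency improvement to the primary analysis, not as a defect of validity. The possible gain is up to about 15% in standard error at R² = 0.3, against a loss of about 1% if the covariate predicts nothing. An appreciable chance imbalance in lung function is quite possible at this sample size, but it matters only to the extent that lung function predicts border time. The conclusion rests on four assumptions: 26 per arm, items 3, 5 and 6 as alternative routes, an R² that the documents do not supply, and a preoperative lung-function value available for all or nearly all patients.

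**What to change.** In the Statistical analysis section, specify that intersegmental border appearance time is analysed by a linear model containing gas group and one continuous preoperative lung-function value from the standard evaluation. FEV1 % predicted is an example, provided it was recorded for all or nearly all patients. State how a missing test is handled, and report the unadjusted t test beside the model. Fix this before the outcome data are examined by arm; if they already have been, label the adjusted model a post hoc sensitivity analysis. No change to the randomization is needed.

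The cost is a short addition to the analysis section, one variable carried into the dataset, one degree of freedom, and about 1% in standard error if the covariate turns out to predict nothing.

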### **Exclusion Criteria:**

1. Patients who are at risk for general anesthesia.
2. Patients with serious mental illness.
3. Pregnancy or lactating women.
4. Active bacterial or fungal infections.
5. Patients with Interstitial pneumonia, pulmonary fibrosis or severe emphysema.
6. Conversion to thoracotomy in surgery.
7. Preoperative assessment of patients undergoing lobectomy.

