## **Surgical Procedures:**

Before anesthesia induction, anesthesiologist placed the electrocardiogram, non-invasive blood pressure, pulse oximetry, bispectral index (BIS) monitor and completed radial artery catheterization successively. All patients were given general anesthesia with double lumen endotracheal intubation. After patients were placed in lateral decubitus position, one-lung ventilation of the dependent lung was initiated with 1.0 of FiO2 (fraction of inspiration) and 5 cm H2O of positive end-expiratory pressure. All patients underwent single-port thoracoscopic surgeries which were performed by the same surgical and anesthesia team. The surgical incision was about 3 cm long and located on the fourth or fifth intercostal space of the midaxillary line.

With the guidance of 3D reconstruction, the targeted segmental bronchi and vessels could be precisely identified and dissected, after that ISP was identified by modified inflation-deflation method. Firstly, anesthesia used fiberoptic bronchoscope to confirm the position and patency of endotracheal tube, suction if necessary. Then the non-dependent lung was re-expanded with airway pressure no more than 20 cm H2O and the flow of gas at 8 L/min, while the dependent ventilated lung was kept on mechanical ventilation without change. The non-dependent lung was re-expanded by pure O2 in O2 group, or by CO2 in CO2 group which was obtained from CO2 insufflator.

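### The exclusion for conversion to thoracotomy has no time limit, so it can remove patients after their allocation is known, and no analysis set keeps them

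*Combined protocol and SAP*

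**What the plan says.** - **Exclusion Criteria, item 6:** "Conversion to thoracotomy in surgery". No time point is attached.
- **Study Protocol:** "This study was a prospective, single-center, open-label, randomized controlled trial".
- **Randomization:** "The patients were randomly assigned to the CO2 group and O2 group at a 1:1 ratio", and "52 opaque envelopes were made according to a random table". Each envelope is to be "opened by operators in surgery, when the structures of targeted segment were successfully dissected and anesthesiologist was about to re-expand the collapsed lung", which is partway through the operation.
- **Surgical Procedures:** after opening, the non-dependent lung is "re-expanded by pure O2 in O2 group, or by CO2 in CO2 group". The section describes every patient as having single-port thoracoscopic surgery and gives no route for a patient who converts.
- **Outcome Measures:** the primary outcome is the time to appearance of the intersegmental border. Secondary measurements continue to 15 minutes after full inflation, and then cover length of operation, drainage, hospital stay, QoR-40 and complications.
- **Statistical analysis:** continuous variables "were analyzed by t test" or an alternative test. The section covers variable types, tests, the significance level and software. It names no analysis set and has no rule for patients excluded after allocation.

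**The concern.** Most of the eligibility list can be checked before the operation. Conversion cannot, because it happens during surgery, and the arm is also revealed during surgery. The words of item 6 therefore cover conversions on both sides of the opening of the envelope.

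A conversion while the envelope is sealed cannot depend on the arm, so removing that patient does not bias the comparison. A conversion after opening is different. The operating team knows the arm, the gas has been given or is about to be, and the exclusion acts on an event that may be influenced by either. For those patients the protection of randomization is lost.

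The outcomes most at stake are the later secondary ones: duration of surgery, drainage, stay, QoR-40 and complications. A converted patient could plausibly do worse on each. The primary outcome is less exposed, because the border may already have been timed when a late conversion occurs. It is affected if conversion comes before the border appears.

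**Working it through.** **1. Reading the sections together.** The order of events is: dissection completed, envelope opened, lung re-expanded with the allocated gas, border timed, measurements to 15 minutes after full inflation, rest of the operation, postoperative outcomes. Item 6 applies throughout the operation, so it reaches past the opening of the envelope. No section limits it, and no section defines an analysis set that retains late converters.

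**2. No stated figure to reproduce.** The plan gives no conversion rate, SD, effect size or sample-size calculation. Everything below is illustrative.

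*Inputs from the documents:* 52 envelopes at 1:1, taken as 26 per arm; two-sided tests at 0.05.

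*Assumptions:* a range of late-conversion rates; k = 1, 2 or 3 patients removed in total; normal outcome; no true difference between arms.

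**3. Chance of at least one late conversion among 52,** 1 − (1 − p)^52:

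| Assumed rate p | Expected number, 52p | Chance of at least one |
|---|---|---|
| 1% | 0.5 | 41% |
| 2% | 1.0 | 65% |
| 5% | 2.6 | 93% |
| 10% | 5.2 | above 99% |

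**4. Type I error of the t test after removal.** There were 200,000 simulated trials per scenario, with 26 v 26 standard normal outcomes and a pooled-variance test. Each patient has a propensity to convert that has correlation ρ with the outcome, and the k highest propensities are removed. In the first row they are taken from all 52 patients; in the others, from one arm only.

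| Scenario | k = 1 | k = 2 | k = 3 |
|---|---|---|---|
| Same rule in both arms, ρ = 0, 0.5 or 1 | 4.9–5.0% | 4.9–5.0% | 5.0–5.1% |
| One arm only, ρ = 0 | 5.0% | 5.0% | 5.0% |
| One arm only, ρ = 0.5 | 5.4% | 6.1% | 6.9% |
| One arm only, ρ = 1 (the worst k) | 6.5% | 9.4% | 13.3% |

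The false shift in the mean is 0.04, 0.07 and 0.10 SD at ρ = 0.5, and 0.08, 0.15 and 0.21 SD at ρ = 1. It is about zero in the other scenarios. Repeat runs agree to within about 0.3 percentage points.

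**5. Complications.** Suppose c of 26 patients in each arm have a complication, and k late converters, all with a complication, are dropped from one arm. The false difference is (c − k)/(26 − k) − c/26. With c = 5 (5/26 = 19.2%):

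- k = 1: 4/25 = 16.0%, difference −3.2 points
- k = 2: 3/24 = 12.5%, difference −6.7 points
- k = 3: 2/23 = 8.7%, difference −10.5 points

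For k = 3 the difference is −11.5 points if c = 3 and −9.0 points if c = 8. Dropping k from both arms creates no difference, but both reported rates fall to 16.0%, 12.5% or 8.7%, so complications are understated.

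**6. Precision.** The standardized difference detectable with 80% power is (1.960 + 0.842) × √(1/n₁ + 1/n₂). This is 0.777 at 26 v 26, 0.785 at 26 v 25 and 0.809 at 24 v 24. Loss of power is not the issue; selection is.

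**The case against.** The strongest reply is that late opening of the envelope already deals with most conversions. Opening waits until dissection has succeeded, so a patient who converts during dissection leaves with the allocation still concealed. On this reading item 6 is simply the last eligibility check before allocation, and the documents report no patient dropped after it. The primary outcome follows directly on re-expansion and is largely spared.

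The size is also open to challenge. One rule applied alike to both arms gives no inflation. The 6.5–13.3% range needs every removal in one arm and perfect correlation with outcome. In the complication example with 5 events per arm, Fisher's exact test gives p = 1.00, 0.70 and 0.42 for k = 1, 2 and 3, so none would be declared significant. Finally, the missing analysis set is a general gap, and the document is dated June 2023 and written in the past tense, so rewording item 6 may change nothing prospectively.

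Much of this stands: late conversions may be few or absent, the primary outcome is mostly protected, and the larger figures are extreme cases. It does not remove the point. The restriction to conversions before opening is not in the text, and describing all patients as having thoracoscopic surgery fits the literal reading better than the lenient one. A distorted complication rate misleads the reader even when it is not significant. An analysis set can still be defined and reported after enrolment has ended.

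One related gap also remains. The Randomization section does not say whether a patient counts as randomized on receiving the envelope or at its opening, or whether an unopened envelope is reused.

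**Conclusion.** The concern holds and should be fixed. As written, item 6 allows exclusion after allocation and treatment in an open-label trial, and nothing in the statistical plan brings those patients back.

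The size is unknown and may be nil. There is no bias unless late conversion both differs by arm and is related to the outcome, and the documents show neither. With one to three removals confined to one arm, type I error is 5.4–6.9% at moderate correlation and 13.3% at the extreme. A complication rate could be off by about 3 to 11 points if the assumed 5 of 26 events per arm applies. These figures assume 26 patients per arm, normal outcomes for the t test, and assumed numbers of late converters. Confidence is medium, because the text is clear but its consequence depends on events the documents do not report.

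**What to change.** - Limit item 6 to conversion to thoracotomy before the envelope is opened.
- In the Statistical analysis section, define the analysis set as every patient whose envelope was opened, in the allocated group, keeping any border time and later outcomes recorded.
- State that a patient counts as randomized when the envelope is opened, and what happens to envelopes left unopened.
- Account for every opened envelope (analysed or not, with the reason) and report late conversions by arm. If there were none, one sentence settles the matter.
- If conversion comes before the border appears, report the time as missing, by arm. A sensitivity analysis giving such patients the worst rank is optional.

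If enrolment is complete, apply this through the analysis set and the report. The cost is a few sentences, with no extra patients and no change to clinical management. Intervals may widen slightly because a few poor outcomes stay in, and data for any late converter already excluded would have to be retrieved from records.
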